### **15.8. Analysis**

The demographics of our prevalence study sample, both non-recent and recent cases, will be initially compared to routine data collected from the 6 sites over the course of the national survey (WP2) in order to assess representativeness of our sample. The final dataset will then be weighted for demographics (e.g. age, gender, deprivation).

A direct estimate of the prevalence of mental health within SARC attendees will be determined from the sample and weighted estimates produced for the 6 SARC sites. Additionally, a further weighted national estimate will be produced (if demographic data can be obtained for all 47 SARC sites).

Analysis of other health, wellbeing and behavioral measures will follow the same principle to produce direct (and site-specific and national weighted) estimates. Prior to producing these estimates, the dataset will be analyzed to determine how/if demographics, site or method of data collection have influenced prevalence measures. A logistic multivariate analysis will be undertaken to determine predictors of mental health and/substance use diagnosis. Participant's feedback on satisfaction with services and any gaps/unmet need will also be analyzed descriptively and themed in order to glean qualitative insights.

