#### **14. WORK PACKAGE 2: THE NATIONAL SURVEY OF SARCS AND MENTAL HEALTH/SUBSTANCE MISUSE**

---

WP2 is a national survey of SARCS examining how they currently respond to mental health and substance misuse which required no ethical approval, or additional consent from participants. As such it is not detailed here. The survey has now been closed. The results have been used to inform case study sampling in WP3 and 4.

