### **15.4. Sample**

Adults over the age of 18 who attend SARCs and who consent to participate within the recruitment period (or until sample size is reached).

The Inclusion Criteria are as follows:

- 1.) Aged 18 or older
- 2.) Can read and understand English (or there are suitable confidential translation services available)

The Exclusion Criteria are as follows:

- 1.) Lack of capacity to provide informed consent.
- 2.) Where participation is deemed to significantly increase risk to self or others.
- 3.) Attendee of a SARC not participating in the study

To meet power requirements, a total sample size of n=360 across the six sites should be obtained (n=60 at each site). With an estimated population of 4000 across 6 sites per year, we estimate attendees at each SARC will be 40-60 referrals per site, per month. In a recent 12-month audit of mental health needs in Thames Valley SARCs (Brooker et al., under review) the SARC staff obtained

consent and collected data on 42% of attendees and 38% declined to participate (with limited support to recruit). Therefore we are confident that we should be able to obtain consent from 50% of attendees to participate which means 20-30 per site, per month. If we assume 20 per month (~50%) consent to participate x 6 sites= 120; therefore, sample size would be reached in 3 months; 120 x 3 =360, with 3 months leeway for variation. Extra sites may be added as necessary.

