#### **16.4 Study Design**

A case study analysis of six SARCs (with the option of adding more if necessary). Selection of the SARCs will be based on a maximum variation, theoretical sampling framework established using evidence from other studies in the research programme (i.e. WP1 - the systematic review, and WP2 – the survey of SARCs).

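### The WP3 'national' prevalence estimate weights six purposively chosen SARCs on demographics alone, so it is a standardised six-site figure and not a national one

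*Protocol*

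**What the plan says.** Protocol section 15.8 first compares the sample with routine data from the six sites. It then states: "The final dataset will then be weighted for demographics (e.g. age, gender, deprivation"). From this come a direct estimate, weighted estimates for the six sites and, in addition, a national one: "a further weighted national estimate will be produced (if demographic data can be obtained for all 47 SARC sites"). No other condition is attached to the national figure. Other measures follow the same principle, with site-specific and national weighted estimates. Before those are produced, the data are to be examined for an influence of demographics, site or collection method; the section does not say what that examination would change.

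Site selection is described elsewhere. Section 12.4 takes about six SARCs from a sampling framework built in WP1 and WP2. Section 14 says of the WP2 survey: "The results have been used to inform case study sampling in WP3 and 4". Section 16.4 gives the method: "Selection of the SARCs will be based on a maximum variation, theoretical sampling framework".

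On numbers, section 15.4 asks for "a total sample size of n=360 across the six sites should be obtained (n=60 at each site"), and says of volume: "With an estimated population of 4000 across 6 sites per year", "we estimate attendees at each SARC will be 40-60 referrals per site, per month". Sections 15.3 and 15.4 allow further sites.

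**The concern.** Two kinds of selection stand between the 360 respondents and the attendees of 47 SARCs: which attendees of a site respond, and which sites are in the study. Demographic weights address the first, as far as response depends on demographics. They do nothing about the second.

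The second matters here because the sites were not drawn at random. They were picked to differ, using a survey of how SARCs respond to mental health and substance misuse, which is close to the subject of the outcome. Section 16.5 (Element 1) itself describes provision as varying greatly. Obtaining demographic data from all 47 centres therefore does not make the figure national, although the protocol treats that as sufficient.

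A smaller question concerns any figure pooled over the six sites. With equal targets and unequal attendance, a small site counts for more than its share of attendees, and no weight for attendance is named.

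**Working it through.** **The plan's own figures.** Section 15.4 expects "we should be able to obtain consent from 50% of attendees to participate which means 20-30 per site, per month". Taking the lower end: 0.5 × 40 = 20 per site per month; 20 × 6 = 120; 120 × 3 = 360 = 6 × 60. The 360 reproduces. The population of 4000 a year is 4000 / (6 × 12) = 55.6 per site per month, inside the 40-60 range.

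**National estimate.**
- Sites sampled: 6 of 47 (12.8%); 41 unsampled.
- Let f be the share of national attendees seen at the six sites, P6 their prevalence and P41 that of the other sites, both after standardising to the same demographics. The national value is f·P6 + (1 − f)·P41, so reporting P6 as national is wrong by (1 − f)(P6 − P41).
- The protocol does not give f. Assuming equal-sized SARCs, 1 − f = 41/47 = 0.872. An assumed difference P6 − P41 of 5 points gives 0.872 × 5 = 4.4 points; 10 points gives 8.7.
- The error is zero only if P6 = P41, which is assured only where prevalence depends on the weighted demographics alone. For comparison, the simple 95% half-width at n = 360 and p = 0.5 is 1.96 × √(0.25/360) = 5.2 points.

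**Between-site variance, for sensitivity only.** SE = √(SD²/6 + (0.25 − SD²)/360), with the between-site SD assumed:
- SD 5 points: √(0.0025/6 + 0.2475/360) = 3.32 points; × 2.571 (t, 5 df) = 8.5 points.
- SD 10 points: √(0.01/6 + 0.24/360) = 4.83 points; × 2.571 = 12.4 points.

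These treat the sites as exchangeable draws, which they are not.

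**Pooled six-site estimate.** A site seeing 40 a month has 480 attendances a year, and one seeing 60 has 720. With 60 respondents each, the sampling fractions are 60/480 = 12.5% and 60/720 = 8.3%.
- Three sites at 40 and three at 60 (assumed split): attendance shares are 120/300 = 0.4 and 180/300 = 0.6, against 0.5 and 0.5 in the sample. Site weights are 0.8 and 1.2, so small sites are over-represented by 1/0.8 = 1.25.
- Shift = (0.6 − 0.5) × gap in prevalence between large and small sites. Gaps of 10, 20 and 29 points give 1.0, 2.0 and 2.9 points. The 29 is the distance between the 40% and 69% quoted in section 12.1; it is used as a wide case and is not evidence of a gap by site size.
- Sizes set to total 4000 a year (40, 53.3 and four at 60), with prevalence rising linearly by 29 points over the size range: 62.6% unweighted against 64.0% weighted, a shift of 1.4 points.
- If prevalence is unrelated to site size, the expected shift is zero.
- Cost in variance (Kish): (0.8² + 1.2²)/2 = 1.04.

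**One site.** 1.96 × √(0.25/60) = 12.7 points before weighting.

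**The case against.** The national figure is additional and conditional. WP3's first aim (section 15.1) is prevalence in a cohort of SARC attendees, not in England. The weighting list is given as examples, detail may lie in an analysis plan not shown, and site is to be examined for at least some of the estimates. These points limit the importance of the finding but do not remove it. The protocol itself says when a national estimate will be produced, and that condition is insufficient. Adding further demographics to an open list would not bring in site selection, and the examination of site has no stated consequence.

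Four stronger readings are tempting, and the documents do not support them:
- *The interval will be too narrow.* No interval or variance method is stated for any prevalence estimate, and this may properly be left to the analysis plan. The half-widths above are illustrations.
- *The six-site figure averages sites rather than attendees and is materially distorted.* The weighted estimates for the six sites can be read as site-specific, where allocation does no harm. If pooled, weighting to the six sites' routine data may recover part of the imbalance. Sixty is a target, actual volumes are not given, and 40-60 may express uncertainty about a typical site. Within that range the shifts calculated are smaller than the 5.2-point sampling half-width.
- *Recent or non-recent assault was wrongly left out of the weights.* Section 15.8 compares the sample on it, and WP4 and WP5 use it in sampling and matching, so including it is sensible. Its absence from a list of examples is not an error.
- *A random site effect, or t on 5 df, would make the estimate national.* It would not. Maximum-variation selection may also inflate the between-site SD, so such an interval is no firmer than its assumptions.

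**Conclusion.** The national label does not follow from the design. Section 15.8 would call a figure national when it comes from six purposively varied SARCs weighted on demographics, with demographic data for 47 sites as the only condition. That is justified only if prevalence depends on the weighted demographics alone, which the protocol neither states nor makes plausible. The size of the error cannot be derived from the protocol: it is 4.4 to 8.7 points for an assumed residual difference of 5 to 10 points between sampled and unsampled sites of equal size, and it could be zero.

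The attendance weight is a minor, secondary improvement: about 1 to 3 points in the balanced 40/60 case for assumed gaps of 10 to 29 points, and zero if prevalence is unrelated to site size. Material distortion of the pooled figure is not shown.

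**What to change.** 1. In section 15.8, replace the term national estimate with a six-site estimate standardised to the national SARC demographic profile. State the assumption that, given the weighted demographics, prevalence does not differ between sampled and unsampled sites. Show the range of the site estimates beside it, noting that each rests on about 60 people (12.7 points either way at p = 0.5). An interval including between-site variance may be added as a sensitivity analysis, with a note that the sites are not a random sample.
2. For any estimate pooled over the six sites, use a site weight (adult attendances divided by respondents) as the base weight and fit the demographic weights on top, so that the final weight is their product.
3. As a suggestion only, include recent or non-recent assault among the weighting variables.

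The cost is wording and analysis code. Attendance counts should come with the routine site data already planned for, though the protocol does not say so. No further data are needed from participants. The downside is a weaker national claim and slightly more variable weights (design effect about 1.04 in the 40/60 case).

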### **15.9. Health Economics**

Little is known about what services SARC attendees use and the related costs. The aims of the health economics analysis in WP3 will be to:

- (i) Provide descriptive statistics of resource use and costs for adult SARC attendees at recruitment and 6 months;
- (ii) Calculate quality adjusted life years (QALYs) over 6 months;
- (iii) Calculate the predictors of costs and QALYs; and
- (iv) Quantify the relationship between costs and QALYs using general linear models.

Resource use will be costed using nationally published sources. In addition to reporting descriptive statistics of service use and costs we will use general linear models using appropriate family and link functions to provide descriptive statistics of predicted costs for different patient characteristics. In particular, we will evaluate the relationship between patient care pathway, costs and quality of life outcomes such as CORE and ReQoL to identify if engagement with services is predictive of better or worse quality of life. QALYs will be calculated from the ReQoL using algorithms currently under development by The University of Sheffield to calculate the area under the curve. We will use the AIC to decide the model structure which variables to include in the models (Barber and Thompson, 2004). For people missing data at 6 months we will evaluate baseline predictors of missing data and use these to construct multiple imputed datasets using chained equations. Final analyses will be conducted on the imputed data datasets.

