### **15.6. Measures**

The following self-complete outcome measures will be used to assess relevant aspects of mental health and substance misuse.

- Demographics questionnaire
- Mental Health symptoms CORE 10 (Connell and Barkham, 2007) (MAIN OUTCOME)
- Alcohol Screening Tool (AUDIT-C) (Bush et al., 1998)
- The Primary Care PTSD Screen for DSM-5 (PC-PTSD-5) (Prins et al., 2015)
- ReQoL (Quality of Life for mental health) (Keetharuth et al., 2018)
- Drug use (DAST) (Skinner, 1982)
- Standard assessment of personality – a brief screen for personality disorder (SAPAS) (Moran et al., 2003)

These measures (with the exception of demographic questionnaire and SAPAS), will be completed again 6 months following recruitment into the study. At the 6 month follow-up, participants will also complete a bespoke service receipt inventory - designed to collect information on the proportion of different mental health, substance misuse and counselling services used by people in contact with SARC's, along with questions regarding participant's satisfaction and perceptions of unmet need. At this time point, participants will also be asked for meta-feedback about how they felt about the recruitment process and their participation in the study.

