After the participant has referred themselves to the study or given verbal consent to be contacted by a researcher, researchers will follow the following processes:

- 1.) Participants name and preferred method(s) of contact will be recorded by the research team. The researcher will contact the participant via phone (or post, email or text) to speak with the participant and if they so wish, provide them with all the information necessary for them to make fully informed consent (1-4 weeks after the presentation at SARC). Written information will be provided if safe to do so in the form of a PIS and this will also be verbally discussed. Participants will be given at least 24 hours (or longer if needed/requested) to consider the information before deciding whether or not to take part.
- 2.) If the participant decides to take part in the study, then fully informed consent will be obtained and the baseline study questionnaires will be completed, usually via a link emailed to the participant using University of Leeds approved online survey provider (e.g. 'Online Surveys'). However, if participants prefer, they can also complete the consent forms and questionnaires by post. In this instance, 2 copies of the consent forms signed by the researcher will be sent to participants along with the questionnaire and a stamped addressed envelope. Participants will be instructed to complete the consent forms and questionnaire, returning 1 consent and the questionnaire in the stamped addressed envelope provided. A further option for completing the questionnaires is over the phone with a researcher. In this

instance, the researcher will complete the online consent form and questionnaire over the phone with the participant, obtaining text or email confirmation of consent.

3.) Participants will be followed up 6 months later (using contact preferences obtained at baseline) in order to complete the follow-up questionnaires and service use questions.

Participants will also be asked for meta-feedback about how they felt about the recruitment process and their participation in the study.

When attempting to contact the service user, researchers will use contact preferences up to 5 times before we record as 'unable to contact', in these instances, personal data will be deleted from the database.

The participants will receive £10 for participation in the prevalence study and follow-up, and if required, reimbursement for any additional travel expenses

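### WP3 promises resource use and costs at recruitment, but the only service-use instrument it describes is given at 6 months

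*Protocol*

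**What the plan says.** Section 15.9 of the Protocol lists four health-economic aims for WP3. The first is to "Provide descriptive statistics of resource use and costs for adult SARC attendees at recruitment and 6 months". The others concern QALYs over 6 months, the predictors of costs and QALYs, and the relationship between the two. On costing, the section says "Resource use will be costed using nationally published sources".

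Section 15.6 introduces the baseline battery with "The following self-complete outcome measures will be used to assess relevant aspects of mental health and substance misuse". It lists seven items: a demographics questionnaire, CORE-10, AUDIT-C, PC-PTSD-5, ReQoL, DAST and SAPAS. On repetition it says "These measures (with the exception of demographic questionnaire and SAPAS), will be completed again 6 months following recruitment into the study". The service-use form comes in only after that: "At the 6 month follow-up, participants will also complete a bespoke service receipt inventory". Its purpose is given as "designed to collect information on the proportion of different mental health, substance misuse and counselling services used by people in contact with SARC's".

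Section 15.7.1 gives the same schedule. At entry, "fully informed consent will be obtained and the baseline study questionnaires will be completed"; at 6 months participants are contacted again "in order to complete the follow-up questionnaires and service use questions".

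**The concern.** The aim needs participant-level service use at two times, and the data collection described gives it at one. This is a matter of what is collected and when, so an analysis plan cannot repair it afterwards.

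The direct loss is the recruitment half of the first aim. There is also an indirect loss. Section 15.9 wants to know which characteristics predict costs and QALYs, and whether engagement with services goes with better or worse quality of life. Without service use before recruitment, a participant already in long-standing care looks the same in the 6-month data as one who reached care after attending the SARC. If people already in care are more unwell, an association between engagement and poor quality of life would be hard to interpret. The same variable would also be absent from the baseline predictors of missingness that section 15.9 intends to use for multiple imputation.

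**Working it through.** No arithmetic figure is in dispute. The check sets the sections side by side and looks for any other source.

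1. **Time points promised** (15.9, first aim): recruitment and 6 months, so 2.
2. **Service-use instruments at baseline** (15.6): none of the seven listed items measures service or resource use, so 0. Section 15.7.1 mentions only questionnaires at this stage.
3. **Service-use instruments at 6 months** (15.6): the service receipt inventory, so 1. Section 15.6 presents it as an addition to the repeated measures, and 15.7.1 mentions service-use questions only at this contact.
4. **Look-back period:** none is stated for the inventory. Its described purpose does not mention any time before recruitment.
5. **Other possible sources:**
   - The nationally published sources in 15.9 can price the services used; they do not show how much of each service a participant used.
   - The routine site data from WP2, cited in 15.8, serve to compare demographics and judge representativeness.
   - The CRIS and Kent SARC records (section 17) belong to WP5 and are anonymised. No link to WP3 participants is described.
   - WP3 describes no extraction from participants' health records.
6. **Result:** data are described for 1 of the 2 promised time points. For recruitment, no source is stated for any of the 360 participants planned in 15.4.
7. **What is not affected:** ReQoL is completed at both times, so QALYs can be calculated. Costs at 6 months rest on the inventory given then. The prevalence estimates use the clinical and substance-use measures, which are all in the baseline battery.

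**The case against.** The strongest defence is that the Protocol does not reproduce its forms. The demographics questionnaire might hold service-use items, or the 6-month inventory might ask about the time before recruitment. That much stands: one cannot say that the aim is impossible to meet, only that no source for it is stated. If either was intended, the sections still need to be brought into line, because 15.6 and 15.7.1 as written point to 6 months alone.

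A reader might go further in three ways that the Protocol does not support.

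- **That the cost models break a promise to adjust for baseline cost.** Section 15.9 makes no such promise. Variables are to be chosen by AIC, and the baseline clinical and demographic measures are available. The models can be run as described; they merely lack one plausible candidate.
- **That separating continuing care from newly reached care is the main question of the study.** It is not among the listed research questions, objectives or WP3 aims. Research question 4 asks about services accessed after attending a SARC. The WP3 aims in 15.1 concern prevalence, needs met at 6 months, and QALYs.
- **That the loss can be sized from the Protocol.** The background section reports that 20% of attendees in one audit had a history of psychiatric admission. That history has no time limit, so it does not measure recent service use, and according to 15.4 the audit collected data on 42% of attendees. The Protocol gives no correlation between earlier and later costs, so any figure for precision lost would rest on assumption alone.

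Burden is also a fair point: extra baseline questions fall on people who may have been assaulted recently.

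**Conclusion.** The inconsistency is real and the rest of the Protocol does not resolve it. Section 15.9 promises resource use and costs at two time points; sections 15.6 and 15.7.1 describe collection at one. The recruitment half of the first health-economic aim has no stated data source, and prior service use is unavailable as a candidate predictor in the cost and QALY models and in the imputation model.

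The reach is limited. One half of one descriptive aim is unsupported and a useful covariate is missing. The main outcome measure, the prevalence estimates, the QALYs and the 6-month costs all stand. The conclusion assumes that the listed baseline measures are complete and that the inventory has no unstated look-back before recruitment. It should be fixed, and the change is small.

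**What to change.** Reconcile 15.9 with 15.6 and 15.7.1 in one of three ways.

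1. **Preferred: add a short service receipt inventory to the baseline questionnaire.** State its recall period and let it run up to recruitment, not only up to SARC attendance. Under 15.7.1 staff may take consent to contact within 6 weeks of attendance, and the researcher gives study information 1 to 4 weeks after presentation. A recall window that ended at attendance, followed by an inventory that started at recruitment, would leave those weeks uncounted. The form should record amounts of contact, since prices alone cannot give a cost. Baseline service use or cost can then be offered as a candidate covariate in the cost and QALY models and in the imputation model. The cost is an amendment and a few more items for a vulnerable group.
2. **Let the 6-month inventory also cover a defined period before recruitment.** This adds nothing at baseline, but recall is longer and less reliable, and participants lost to follow-up give no such data.
3. **Remove recruitment from the first aim** and state that prior and new service use cannot be separated. This is a change of wording only, and it gives up the information.

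Whichever is chosen, the recall period of each service-use form should be written into 15.6.

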### **15.3. Setting**

Participating SARCs at 6 sites across England, with the possibility of adding further sites if needed

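### Section 15.9 leaves site to AIC selection in the models relating care pathway to costs and quality of life, although the six sites were chosen to differ; site should be kept in regardless of AIC

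*Protocol*

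**What the plan says.** **The models.** Protocol 15.9 plans generalised linear-type models, with family and link to be chosen, for costs and QALYs. In particular, "we will evaluate the relationship between patient care pathway, costs and quality of life outcomes such as CORE and ReQoL", to learn whether engaging with services predicts better or worse quality of life. The only stated rule for model content is AIC, which is to settle both structure and variables. Section 15.9 names no site term, random effect or clustered standard error. It does not exclude them either.

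**The sites.** Section 15.3 has "Participating SARCs at 6 sites across England, with the possibility of adding further sites if needed". Section 12.4 describes one set of about six case study SARCs drawn from a framework built on WP1 and WP2. Section 14 says of the WP2 survey that "The results have been used to inform case study sampling in WP3 and 4". Section 16.4 gives the principle: "Selection of the SARCs will be based on a maximum variation, theoretical sampling framework established using evidence from other studies in the research programme". Section 16.5 describes service provision across SARCs as highly variable.

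**Where site is considered.** Section 15.8 plans site-specific estimates, and before producing them "the dataset will be analyzed to determine how/if demographics, site or method of data collection have influenced prevalence measures". Nothing carries that step into the 15.9 models.

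**The concern.** When sites are selected because their services differ, site is a likely common cause of pathway and outcome. It helps determine which services a participant can reach. It may also go with differences in case-mix, deprivation and service supply that bear on costs, CORE and ReQoL. A pathway coefficient from a model without site mixes the association inside sites with differences between six areas. Its standard error also treats participants in one site as independent.

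AIC does not guard against this. It asks whether site improves the fit of the outcome model enough to pay for its parameters, and takes no account of how strongly site is tied to pathway. A site effect that is modest for the outcome but closely linked to pathway can therefore be removed, and that is a case where its removal biases the pathway coefficient.

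At stake is the WP3 answer on whether engagement goes with better or worse quality of life. Section 17.6 also draws on the WP3 analysis for the WP5 costing.

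**Working it through.** **1. The plan's own figure.** Section 15.4 reaches its total by recruitment arithmetic: "sample size would be reached in 3 months; 120 x 3 =360, with 3 months leeway for variation". Check: 20 per site per month × 6 sites × 3 months = 360, and 360 / 6 = 60 per site. It reproduces. No ICC and no six-month retention figure is given, so both are assumed below: 60 per site (everyone followed up) and 36 per site (60% followed up).

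**2. How often AIC drops site.** With six sites, site costs 5 parameters, so AIC drops it when the gain in twice the log-likelihood is below 2 × 5 = 10. With m participants per site and outcome ICC ρ, that gain is roughly [1 + mρ/(1−ρ)] times a chi-square on 5 df. So

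P(drop) ≈ P(χ²₅ < 10 / [1 + mρ/(1−ρ)]).

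| m | ρ | 1 + mρ/(1−ρ) | Threshold | P(drop), formula | P(drop), simulated |
|---|---|---|---|---|---|
| 60 | 0.02 | 2.22 | 4.50 | 52% | 50-55% |
| 60 | 0.05 | 4.16 | 2.41 | 21% | 20-24% |
| 60 | 0.10 | 7.67 | 1.30 | 7% | 7% |
| 36 | 0.02 | 1.73 | 5.76 | 67% | 66-68% |
| 36 | 0.05 | 2.89 | 3.45 | 37% | 38-39% |
| 36 | 0.10 | 5.00 | 2.00 | 15% | 15-18% |

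The simulated column uses a binary pathway whose log-odds vary between sites with SD 0.5 to 2.0. With the tie expressed as a pathway ICC of 0.2-0.5, the range for ρ = 0.02-0.05 and m = 36-60 is about 23-68%, the same within simulation error.

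**3. Effect on the pathway test.** Setting: 6 sites × 60, normal outcome, linear model, true pathway effect zero, 4,000 datasets per row. Entries are two-sided rejection rates at nominal 5%.

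| Pathway ICC | Outcome ICC | Site never offered | AIC decides on site | Site always kept |
|---|---|---|---|---|
| 0.2 | 0.02 | 7.3% | 6.2% | 5.1% |
| 0.2 | 0.05 | 10.6% | 5.9% | 4.8% |
| 0.5 | 0.02 | 10.6% | 8.9% | 5.5% |
| 0.5 | 0.05 | 18.9% | 7.9% | 4.9% |
| 0.5 | 0.10 | 28.3% | 6.5% | 5.4% |

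The Monte Carlo standard error near 8% is √(0.08 × 0.92 / 4000) = 0.4 points. Repeat runs, including 36 per site, put the AIC column at about 6-8% and the top of the never-offered column at about 29%.

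**4. Plausibility of the never-offered column.** The approximate design effect for a pathway that varies within site is 1 + (m−1) × ICC_outcome × ICC_pathway. At m = 60, 0.05 and 0.5 it is 1 + 59 × 0.025 = 2.48, so the standard error is too small by a factor √2.48 = 1.57. At 0.02 and 0.2 it is 1 + 59 × 0.004 = 1.24, a factor of 1.11.

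**5. Where the excess under AIC arises.** It comes from the datasets in which site is dropped. Where pathway is strongly tied to site, the rejection rate within those datasets is about 8-19%. AIC protects well when site differences in the outcome are large, and least when they are modest.

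**The case against.** **Silence is not exclusion.** Section 15.9 gives no covariate list, and such lists are commonly left to an analysis plan. A reader might infer that the models pool the sites with site left out, so that between-site differences will be reported as pathway effects with intervals that are too narrow. The text does not support that: site may be a candidate, and AIC would usually keep it if site differences were large. What remains is that the protocol does fix a selection rule and exempts nothing from it. An analysis plan that forced site in would depart from that rule.

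**The large error rates belong to other models.** The 7-29% range needs site never to be offered. A further calculation treats pathway as wholly fixed by site: the design effect 1 + 59 × ICC is 2.18 to 3.95 at ICC 0.02-0.05, with false positives of about 18-32%. But service use is collected per participant (15.6), and 15.9 names no site-constant exposure. Neither range describes the stated plan.

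**Area differences in unit costs.** These might be suspected as a further confounder, but 15.9 costs resource use from national published sources.

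**Section 15.8 does examine site.** True, and it weights for demographics, but this does not adjust the 15.9 models. The point is also confined to 15.9; nothing here was worked out for the 15.8 predictor model.

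**No test is stated in 15.9, and the programme is interested in context.** Both are fair. The false-positive rate serves here as a yardstick for whether an interval can be trusted. Keeping site does restrict the coefficient to within-site contrasts. A random effect or a clustered analysis is an alternative, though six clusters support either poorly.

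**Conclusion.** The point holds as a weakness in a stated rule. Section 15.9 lets a fit criterion decide on every variable, including site, in models whose main interest is a pathway that the site selection ties to site. Under the stated rule the damage is modest: about 6-8% false positives instead of about 5%, with site dropped in about 23-68% of datasets.

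These figures rest on assumed ICCs (outcome 0.02-0.05, pathway 0.2-0.5), 36-60 followed up per site, six equal sites, site being offered to AIC, and a linear model with a normal outcome. Cost models with another family and link could behave somewhat differently. Confounding and narrow intervals are a conditional risk, not something the protocol commits to. The change is still worth making, because it removes the risk at little cost.

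**What to change.** Add to 15.9:

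- Site is kept as a fixed term in every model relating pathway or engagement to costs, QALYs, CORE or ReQoL, and is exempt from AIC selection. AIC may still choose the family, link and other covariates.
- Pathway and engagement coefficients are reported as within-site associations.
- Any pathway feature that does not vary within a site is described across sites without a test.

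**Cost.** The number of sites minus one parameters: 5 out of up to 360 participants with six sites, a few more if sites are added as 15.3 allows. Site-constant features get no coefficient, but six sites could not support one anyway. If the team also wants the between-site contrast for its realist work, it can present it descriptively beside the within-site result.
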